#### Overview

Potential participants will complete a telephone and an in-clinic screening to determine eligibility for this study. Eligible participants will be randomized to receive one of two treatment conditions: 1) Zonisamide plus *Take Control* (a computerized alcohol reduction and medication compliance program developed by the National Institute on Alcohol Abuse and Alcoholism (NIAAA)); 2) a placebo plus *Take Control*. For both conditions, participants will receive 12 treatment sessions. Participants will receive medication at each session, and they should have two weeks worth of medication on hand at any given time. Participants will take the medication as prescribed at home. The first 11 treatment sessions will include *Take Control*. The 12 treatment sessions will be followed by two drug dose taper sessions, and a follow up phone interview immediately following the final session.

Participants will also undergo two scans of less than 2 hours duration, one before they begin study sessions and the second near the end of the study (12th study week and before the medication taper). At the in-clinic screening session, participants will receive a “MRI Information for Research Participants” handout that answers some commonly asked questions about MRI and tells participants what they can expect while undergoing an MRI scan. Both scans will be conducted at BU CILSE. Participants will be screened before each scan session for pregnancy (urine sample, women of childbearing potential only), recent smoking or alcohol use (breathalyzers), and illicit substance use (urine sample). Participants will be asked to complete the Alcohol Urge Questionnaire (AUQ) before and after the scan. Participants will also be asked to complete item #8 from the AUQ before and after the Alcohol Cues Task. Eligible participants will complete a 1-hour 3 Tesla MRI scan involving structural imaging (MRI) and functional imaging (fMRI). The fMRI scans include a resting-state scan (no task involved) a cognitive (Stroop) task, and an alcohol cue reactivity task. The latter two scans involve presentation of visual images to participants while they are in the scanner. No contrast agent or invasive procedures are used. Only personnel trained in working in high magnetic field environments will work on this project. Imaging data will be analyzed on secure networks using only encrypted files. All data obtained will be coded to protect participant privacy and confidentiality.

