**I. Rogers Risk Task** - In this online task, participants are assigned a certain number of points to begin with and are instructed to make decisions that will increase their total score. They are then presented with tasks that involve gambling their points. For example, they are presented with red and blue boxes and told that one box contains a yellow ticket. If they choose a red box that has a yellow ticket, they will gain 30 points, but if they choose a red box that does not have the yellow ticket, they will lose 30 points. If they choose a blue box that has the yellow ticket, they will gain 70 point, but if they choose a blue box that does not have the yellow ticket, they will lose 70 points. Participants' speed of decision-making and choice are used to measure their willingness to take risks (Rogers, 1999).

**J. Stroop Task** - The Stroop tasks will be shown to subjects using a behavioral experiment software called E-Prime. During the task, neutral words and alcohol-related words will be projected on the screen in different color fonts. Participants will be instructed to press a color button on a button box that correspond to the color of the font of the word on the screen. There are four colors on the button box, which are red, blue, yellow, and green. Four blocks of stimuli all of which include alcohol related (e.g. bar, vodka) words, color (e.g. blue, green) words and neutral words (e.g. years, minute). There is a practice run of the stroop task to get participants used to using the button box, which takes about 2 minutes. Then there goes the actual stroop task, which takes about 7 minutes.

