**K. Alcohol Cues Task** - The Alcohol Cues Task entails the presentation of five sets of images, with both neutral and alcohol-related images. These cues will be shown to subjects using a behavioral experiment software called E-Prime. Subjects will be instructed to look at the images on the screen in the MRI scanner. There are five runs of the task. In the beginning of each run, participant will see "Get Ready" on the screen. There are 22 pictures in each run. In each run, participant will see a fixation cross for a varied amount of time from 6000 milliseconds to 14000 milliseconds followed by the presentation of an alcohol image or a neutral image for 4000 milliseconds. In each run there are 2 images with animals in it. Participants are instructed to press a red button on a button box each time they see an animal that is not a human on the screen. The entire task takes approximately 40 minutes to complete.

**Table 1.** *Schedule for assessments and interventions for the Screening Period, Treatment Weeks 1-12, Dose Taper weeks 13 and 14, Follow-Up week 16.*

*Assessments for week 1 occur prior to the start of treatments.*

*Cmeds/AE=Concomitant Medications /Adverse Events, CIWA-AR=Clinical Institute Withdrawal Assessment for Alcohol Use*

Assessment	S C	1	2	3	4	5	6	7	8	9	1 0	1 1	1 2	1 3	14	15	16
Medical /Biological Assessment																	
Medical History	X																X
Birth Control	X	X			X				X				X				
Vitals/Weight	X	X	X	X	X	X	X	X	X	X	X	X	X	X	X	X	
BAC	X	X	X	X	X	X	X	X	X	X	X	X	X	X	X	X	
Pregnancy Test HCG	X	X	X	X	X	X	X	X	X	X	X	X	X	X	X	X	
Urine Drug Screen	X	X			X					X			X				
Urine EtG		X											X				
Blood Lab Tests	X	X		X	X		X		X		X	X	X				
Pill Count			X	X	X	X	X	X	X	X	X	X	X	X		X	
Portland Neurotoxicity Scale		X	X		X		X		X				X				
CMeds/AE	X	X	X	X	X	X	X	X	X	X	X	X	X	X		X	
CIWA-AR	X	X	X		X		X		X				X		X		
Zonisamide										X							
Clinician Interviews																	
ADIS-5	X															X	
MINI Suicidality	X	X	X	X	X	X	X	X	X	X	X	X	X	X	X	X	
TLFB	X	X	X	X	X	X	X	X	X	X	X	X	X	X	X	X	
Questionnaires																	
Demographic	X																
BDI-II		X											X				
ADS	X																
OCDS	X			X					X			X				X	
AUQ	X			X					X			X				X	
CGI-S & CGI-I	X	X	X	X	X	X	X	X	X	X	X	X	X	X	X	X	
DASS	X												X				
BES	X												X				
MEAQ	X												X				

	ASI	X									X			
	RTCQ	X									X			
	PID-5-BF	X									X			
	PAI-BOR	X									X			
	ISAS	X												
	Q-LES-Q	X									X			
	WSAS	X									X			

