#### Data Analysis

1. Demonstrate that ZON will attenuate changes resulting from performance on alcohol-word and negative-word Stroop tasks in the activity of frontal-parietal and midbrain regions and the connectivity to networks associated with these regions in AUD subjects. Our working hypothesis is that midbrain activity will be lower in ZON treated subjects than in placebo subjects following performance on alcohol and negative emotion Stroop task, which will occur in association with enhanced mid-brain-frontal connectivity and increased synchrony.

Fixed effects models will be used to analyze data for brain activation in regions of interest, with treatment group as a between group factor and Stroop task type and order of stimuli presentation will be within subject factors. Regions of interest will include parahippocampal gyri, midbrain substantia nigra and red nucleus, dorso-lateral prefrontal cortex, and cerebellum.

Connectivity will be assessed using the Free Surfer analysis described below. Seeds will be used for the dorsolateral prefrontal cortex and the midbrain (substantia nigra) following Muller-Oehring et al. (2013).

2. Demonstrate that ZON administration attenuates the enhanced regional brain activity and craving- induced by exposure to alcohol related cues in AUD subjects. Our hypothesis is that exposure to alcohol-related cues will increase brain activity in select limbic and prefrontal areas to a lesser degree in ZON as compared to placebo treated AUD subjects.

Fixed effects models will be used to analyze data for brain activation in regions of interest, with treatment group as a between group factor and stimulus type and order of stimuli presentation was within subject factors. Regions of interest, based on the meta-analysis of Schacht et al. (2013), will include the ventral striatum, medial prefrontal cortex, and the anterior cingulate cortex.

3. Demonstrate that the ZON induced changes in brain activity are predictive of reduced ethanol consumption.

Logistic regression analysis will be used to evaluate zonisamide-induced decreases in the BOLD response in the ventral striatum and the medial prefrontal cortex as predictors of complete abstinence or reduction to safe drinking levels (defined as consumption of no more than more than 2 standard drinks per day) during study weeks 10 to 12.

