#### Imaging Acquisition and Processing:

#### **BOLD RESPONSE- Image Acquisition**

Functional images will be acquired on a Siemens Prisma 3T scanner using a 64-channel phased array headcoil. Blood oxygenation level-dependent (BOLD) contrast will be measured using a gradient echo-planar T2\* weighted imaging sequence (TR = 2000 ms, TE = 28 ms, EPI factor = 47). The images will contain 36 axial slices and each slice will be 64 x 64 pixels. The voxel size will be 3 mm x 3 mm x 3 mm. T1-weighted structural images will also be obtained in the same session along with a brief EPI sequence acquired with oblique slices to ensure the integrity of right and left throughout image format conversion. All images will be converted to FSL-NIfTI format prior to our model-based analysis and the integrity of left and right for each subject will be confirmed.

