#### **Analysis**

The images will be analyzed using FSL 4.1.1 with the FMRI Expert Analysis Tool (FEAT) v5.98 (Smith et al., 2004; Jenkinson et al., 2012). FSL's general linear model will be used to

model each subject's BOLD response to each explanatory variable (EV). The fMRI data will be co-registered to MNI space and regions of significant activation will be determined through using the Harvard-Oxford Structural Atlas included with FSL (Makris et al., 2006; Frazier et al., 2005; Desikan et al., 2006; Goldstein et al., 2007). In second and third level analyses, we will use cluster thresholding with a Z threshold of 2.3 and a cluster p threshold of 0.05. We will use a fixed effects model for these analyses. All analyses of the fMRI data will include active task > control condition contrasts as well as control > active task contrasts as a reality check.

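### The FEAT plan sets fixed effects at both higher levels and exempts neither, so any zonisamide-versus-placebo map made there would leave out between-subject variance

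*Combined protocol and SAP*

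**What the plan says.** The Analysis text under Imaging Acquisition and Processing (Section L) first fits a general linear model to each subject's BOLD response. It then places the inferential thresholds: "In second and third level analyses, we will use cluster thresholding with a Z threshold of 2.3 and a cluster p threshold of 0.05". The next sentence sets the model: "We will use a fixed effects model for these analyses". Neither level is exempted, and no mixed- or random-effects model appears anywhere in the imaging text. The contrasts named there are active task against control and the reverse. The section does not say which level, if any, compares the arms.

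Treatment group appears in the activation models for items 1 and 2 of Data Analysis: "Fixed effects models will be used to analyze data for brain activation in regions of interest, with treatment group as a between group factor". Task or stimulus type and presentation order are the within-subject factors. No subject effect, error stratum or covariance structure is given.

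On the number of levels available inside a subject, the Overview says "Participants will also undergo two scans of less than 2 hours duration". For the alcohol cues task, "There are five runs of the task". For the Stroop, after a practice run: "Then there goes the actual stroop task, which takes about 7 minutes".

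**The concern.** The Study Summary says the scans serve to compare brain activity between the two arms. People were randomized, and the claim concerns people with alcohol use disorder, so the standard error of a between-arm difference must include how much true activation varies from person to person. A fixed-effects higher-level model uses only the within-subject error carried up from the first level.

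If the arms were compared that way and zonisamide did nothing, a treatment difference would be declared too often whenever people differ. A positive map would describe only the people scanned. The activation hypotheses are among the trial's main claims about mechanism, so the level that compares the arms needs a stated and valid error term.

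**Working it through.** **1. The plan's own imaging power.** Inputs from Power Analysis: effect size 0.7, 40 per group, stated power 0.88. Alpha 0.05 is taken from the same paragraph, and two-sided testing is assumed. The expected z is 0.7 × √(40/2) = 3.130, and the power is Φ(3.130 − 1.960) = Φ(1.170) = 0.879. The noncentral t version gives 0.871. Both reproduce 0.88; one-sided testing gives 0.93 and does not. The calculation therefore treats the subject as the unit.

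**2. Size of a fixed-effects comparison of arms.** Let r be the between-subject variance divided by the within-subject variance of one subject's contrast estimate. The true standard error of the arm difference is √(1 + r) times the fixed-effects one. Hence:

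- two-sided error at nominal 0.05 = 2 × [1 − Φ(1.96/√(1 + r))]
- one-sided voxel rate at the plan's threshold = 1 − Φ(2.3/√(1 + r))

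The documents do not give r, so a range is assumed.

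| r | √(1 + r) | 1.96/√(1 + r) | error at nominal 0.05 | 2.3/√(1 + r) | voxel rate at Z 2.3 |
|---|---|---|---|---|---|
| 0 | 1.000 | 1.960 | 0.050 | 2.300 | 0.011 |
| 0.25 | 1.118 | 1.753 | 0.080 | 2.057 | 0.020 |
| 0.5 | 1.225 | 1.600 | 0.110 | 1.878 | 0.030 |
| 1 | 1.414 | 1.386 | 0.166 | 1.626 | 0.052 |
| 2 | 1.732 | 1.132 | 0.258 | 1.328 | 0.092 |
| 4 | 2.236 | 0.877 | 0.381 | 1.029 | 0.152 |

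Simulation with 40 per arm agrees for the fixed-effects test: 0.110, 0.166, 0.259 and 0.381 at r = 0.5, 1, 2 and 4. A t-test on one value per subject stays between 0.048 and 0.052.

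**3. Cluster level (sensitivity only).** Null Gaussian fields were generated on the planned grid ("The images will contain 36 axial slices and each slice will be 64 x 64 pixels", with 3 mm voxels). The cluster cutoff was set to give 0.05 at r = 0. The mask was an assumed ellipsoid, smoothness was assumed at 6 to 10 mm, and r was assumed uniform across the brain. The chance of at least one false cluster for a single one-sided contrast was 0.30 to 0.50 at r = 0.25 and 0.71 to 0.96 at r = 0.5.

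**4. Which levels could lie within a subject.** The cues task has five runs at each of two scans, so combining runs and then scans could use up both higher levels within a subject. The Stroop fits this less easily. If its 7 minutes are one run, only the two scans remain to be combined, and a third level would have to cross subjects.

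**5. The region-of-interest models.** The error rate depends on the test and on the unstated error term.

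- *Group main effect.* Pooling m values per subject with intraclass correlation ρ and no subject term gives 2 × [1 − Φ(1.96/√(1 + (m − 1)ρ))]. This is 0.074 at m = 2, ρ = 0.2 and 0.446 at m = 8, ρ = 0.8.
- *Group by stimulus.* Suppose the values are treated as independent, stimulus response does not vary between subjects, and the subject-intercept variance equals the residual variance. The error variance is then doubled, and the size is 2 × [1 − Φ(1.96 × √2)], about 0.006 (0.007 in simulation).

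The error can therefore go either way.

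**The case against.** The strongest defence is that both higher levels lie inside a subject, where fixed effects is acceptable. The Analysis section names only task-versus-control contrasts, which are within-subject, and names no treatment contrast. The Stroop argument is not conclusive either: the task description mentions four blocks, and Data Analysis speaks of more than one Stroop task type, so separate runs are possible. The documents do not settle this, and a reader should not infer that the plan definitely commits to a fixed-effects treatment map. What remains is that the sentence covers both levels without exception. On the within-subject reading, the arms would be compared in the region-of-interest models, which also carry the fixed-effects label.

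A reader might also infer that those region-of-interest models are wrong. That is not supported. Between-group and within-subject factors are ordinary repeated-measures language, which normally carries a subject error stratum, and the label may simply describe group, task and order. The power calculation also points to the subject as the intended unit. These models are underspecified, not shown to be in error, and step 5 gives no single direction.

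Finally, the cluster figures could be read as near-certain false positives. They rest on an assumed ratio, mask and smoothness, and they describe a whole-brain search, whereas the activation hypotheses name specific regions.

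**Conclusion.** The concern holds for any FEAT comparison of the arms at the second or third level. As written it would use fixed effects, and its type I error would exceed nominal for any between-subject variance above zero. That direction does not depend on the size of the ratio. The amount does: 0.08 to 0.38 for a nominal two-sided 0.05, and 0.020 to 0.152 for a nominal voxel rate of 0.011, over assumed ratios from 0.25 to 4. The cluster rates are sensitivity figures only.

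The point is conditional on the arms being compared at those levels, which the section leaves open. No error is claimed for the region-of-interest models, only a missing statement. The CONN connectivity analysis has its own second-level model and is not affected; nor is the drinking analysis, which is specified as a repeated-measures mixed model. The imaging sample size is not in question.

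**What to change.** In the Analysis section, replace the fixed-effects sentence with:

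> Fixed effects will be used only to combine or difference runs and scans within a subject. Every between-arm comparison will use a mixed-effects model with subject as a random effect.

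This keeps fixed effects available for combining or differencing one subject's two scans.

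As a linked clarification in items 1 and 2 of Data Analysis, replace the fixed-effects label with a mixed model that has a subject random effect, adding subject-by-stimulus variance where the test is group by stimulus. A simpler alternative is one task-minus-control value per subject per scan.

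The cost is wording and one software setting. No new data and no larger sample are needed, since the stated power of 0.88 is already that of a subject-level two-group test. P-values in any FEAT between-arm map would become larger, so some clusters may no longer pass. For the region-of-interest models the direction of change cannot be stated in advance.

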## CONNECTIVITY

### FreeSurfer Analysis

All of the subject's MRI scans will be processed using FreeSurfer. FreeSurfer is a software application developed by the Martinos Center for Biomedical Imaging by the Laboratory for Computational Neuroimaging (*FreeSurfer Wiki*, 2014). FreeSurfer's package of tools for visualization of structural and functional brain data will be used to analyze this data set. The FreeSurfer 'recon-all' tool, which is a fully automated structural imaging stream that runs 30 steps will be used to execute all of the volumes and surface processing pipelines (*FreeSurfer Wiki*, 2014). The FreeSurfer recon-all pipeline contains steps for: motion correction, intensity normalization, talairach transformation, skull stripping, segmentation of the cortex, subcortex and white matter, to generate surfaces and create spherical and flattened representations. There are three automated atlases in FreeSurfer's recon-all script for cortical segmentation and labeling: Desikan-Killiany, Destrieux and DKT40 atlas. In this study we will use the Desikan-Killiany atlas.

The Freesurfer GUI Freeview will be used to model the subject's brain scans in 2 dimensional and 3 dimensional space in order to inspect the recon-all processing output. The topical defects that occur and need to be fixed with Freeview are white matter and gray matter subcortical segmentation, and the corresponding processing step in the recon-all pipeline is re-run for correction.

Resting state DICOM scans will be converted to Nifti files with MRIcron's *dcm2nii* in order to be processed in The Functional Connectivity Toolbox 2014 (CONN). CONN is a Matlab-based cross-platform software that will be used to compute, analyze the functional connectivity of fMRI (Whitfield-Grabrielli and Nieto-Castanon, 2012). The CONN toolbox uses Matlab version 2012 and SPM8 to process the resting-state fMRI scans into ROI-to-ROI connectivity matrices, test hypotheses and visualize data (Whitfield-Grabrielli and Nieto-Castanon, 2012). CONN uses a seed-driven RSFC analysis strategy, where the pearson's correlation coefficient is calculated between the seed time course and the time course of all other voxels (Whitfield-Grabrielli and Nieto-Castanon, 2012). The correlation coefficients are converted to normally distributed scores using Fisher's transformation to allow for second-level General Linear Model analysis (Whitfield-Grabrielli and Nieto-Castanon, 2012). The correlation maps depend on the specific location of the seed so that functionally and anatomically heterogenous ROI are dissociated in order to delineate functional anatomy in the brain by sharp transitions in correlation patterns that signal functional boundaries across the cortex (Whitfield-Grabrielli and Nieto-Castanon, 2012).

The subject's processed MPRAGE scans are imported into CONN, and used alongside the resting state scans. CONN uses CompCor strategy for spatial and temporal preprocessing to

define and remove confounds in the BOLD signal to prevent the impact of physiological noise factors and motion in the data (Behzadi et al., 2007). The CompCor strategy is unique because it is more flexible in its characterization of noise (Behzadi et al., 2007). CompCor models the influence of noise as a voxel-specific linear combination of multiple empirically estimated noise sources, which are estimated from the variability in the BOLD responses within noise ROIs (Behzadi et al., 2007). This is important for the removal of fMRI noise because cardiac and respiratory effects do not have a common spatial distribution in their effects. The removal of this richer characterization of the range of voxel-specific noise effects and additional movement along with temporal filtering and windowing the BOLD signal at each voxel protects against confounds in RS-FC without introducing artifactual biases in connectivity measures.

CONN creates subject-specific ROI files and registers them to the subject space. 99 ROIs will be used as the seeds of interest for whole-brain subject-specific ROI-ROI connectivity analyses.

**Power Analysis:** Power analysis for drinks consumed per day during the last three weeks of treatment were determined using data for the placebo and zonisamide groups from our previous study (Knapp et al., 2015). A power value of 0.9 was found for a group size of 40, with alpha=0.05, and with an effect size of 0.74. In our previous study of ZON approximately 20% of subjects dropped out before week 12 of the study. Consequently, we will randomize 50 subjects per group to reach a target of 40 subjects in week 12 of the present study. Based on data reported by Rubio et al. (2009) for errors of commission on the CPT, a measure of impulsivity, a power value of 0.97 would be obtained for an alpha value of 0.05 for a group size of 40. Based on the findings of Myrick et al., (2008) for the difference between the activation of the ventral striatum for placebo and naltrexone groups a power of 0.88 was seen for an effect size of 0.7 for a group size of 40.

**Safety Analysis:** For safety, subjects will be assessed as having had any serious adverse event during the treatment period or not, and additional analyses will be done by separate types of adverse events. Tolerability will be assessed as a subject being able to continue on the study drug for the entire study duration without requiring discontinuation. The safety and tolerability of the study medications will be first assessed using contingency tables and chi-square tests. Fisher's exact test will be employed for rare adverse events. The chi-square analysis will be followed by logistic regression analyses, adjusting for the stratification factor. Time to drug discontinuation for serious adverse events and time to withdrawal from the study for any reason will be assessed using Kaplan-Meier survival curves and compared between study treatments using the log rank test. Poisson regression will be used to evaluate the rate of serious adverse events by arm stratified by the time periods of dosage escalation, dosage maintenance, and dosage taper.

**Covid-19 Protocols:** Since the beginning of the pandemic in April, 2019 we have modified our protocol in order to minimize the risk of participants contracting and/or spreading Covid-19. Study procedures are no longer taking place at CARD. Instead, all study sessions are being conducted remotely via a HIPAA-compliant Zoom platform. There is no physical contact between study personnel and study participants. The following changes have been made to the protocol described above to preserve study integrity while also reducing participant risk:

- No study procedures, including medical procedures, take place at CARD.
- Participants are required to visit Quest Diagnostic Centers upon screening and roughly every other week during the acute treatment phase. During these sessions participants have their blood drawn and their urine sampled.
- Prior to their screening sessions, participants are mailed a breathalyzer that is used to measure their blood alcohol content, as well as a blood pressure cuff which they use at every visit. They use the breathalyzer prior to signing consent and prior to every study session. The breathalyzer reading is shown to study personnel via Zoom.

